4.7 Data management

Only authorised personnel acknowledged and approved by the Human Research Ethics Committees will have access to study data. All study files will be retained for a minimum of 15 years at respective study sites in accordance with the Australian Code for the Responsible Conduct of Research. The final evaluation dataset will be archived at the completion of the project resulting in a single primary data source being retained at the University of Newcastle.

4.7.1 Community Pharmacy Data

Participating pharmacies will record the patient consultation data in a software application (MedAdvisor) installed in each pharmacy. The data are stored centrally on a secure server hosted by MedAdvisor. MedAdvisor will generate an extract of community pharmacy data, and this will be transferred securely to the research team (University/The George Institute) via one of the following ways:

- 1) Shared via an AWS S3 and The George Institute/University provided with an Access Key/Secret Access
- 2) Machine-to-Human e.g., a csv that is sent via secure message platform Kiteworks.

Data files will include patient identifiers (Medicare number, patient name, contact details and date of birth), the study identification number, and information collected at the registration visit. Upon receipt of data transfers, the George Institute research team will store the data files on secure servers (more detail below).

4.7.2 Participant self-reported data

7-day follow-up visit data will be collected on GDS case report forms hosted by the George Institute. Participants will be identified only by their study identification number and no identifying information will be collected on these forms.

4.7.3 Participant interviews

Participants will be asked during their consenting process if they may be contacted by the research team with an invitation to participate in an interview. It is not expected that interview topics will cause any harm or distress to participants. During interviews if a participant does experience discomfort from the topics discussed or recollection of their health care experiences, they can ask to stop or pause the interview or skip any questions. If patient/carer participants raise any concerns or have question about symptoms or their health care, they will be directed to discuss this with their usual health care provider or a patient support line. To minimise inconvenience participants will be i) invited to complete the interview at a time best suited to them; ii) patients/carers will be offered a voucher of \$20 in recognition of the time taken out of their usual day to participate. Private providers such as Pharmacists and GPs will be offered a \$50 voucher for their time, while public health providers, and administrative and service managers will be interviewed within standard working hours, requiring no further compensation as standard practice.

4.7.4 Implementation data

Practice change checklists: Data from the checklists developed by Practice Change Facilitators will be entered into Redcap. A deidentified file including only pharmacy identification number will be securely sent by the UoN research team to the George Institute for analysis.

Interviews: Lists of patient participants that expressed they are willing to be contacted for an interview on the consent form will be generated. A diversity sample will be constructed from these lists to include a range of socio-economic status, living situation (independent/ other), morbidities and engagement with the initiative. Lists of health system administrators and providers will include those directly or indirectly involved in the initiative. The study team will contact eligible participants to invite them to participate and request a time for an interview/focus group. Non-responding eligible participants will be followed up a maximum of two times. At the scheduled interview all participants will be given a full explanation of the study by the research team and provided with an opportunity to ask questions. Consenting participants will be allocated the unique study ID number generated at the baseline registration visit. Interview data will include files of audio and video recordings and transcripts of interviews/focus groups. Audio or videoconference files of interviews will be transcribed verbatim by a professional transcription service after a confidentiality agreement has been signed.

4.7.5 NSW Health Data

The George Institute will provide NSW Health with a list of study participants recruited at each site. This will include a study identification number generated at registration into the trial and the following identifiers: name, date of birth, address. NSW Health will then extract information for these participants on the variables listed in Appendix 28. The data period will include 12 months prior to the study registration date up to the most recent data available in the NSW Health data collections. A deidentified file including only the participant study ID number will then be sent to the George Institute for Global Health using a secure file transfer protocol.

4.7.6 MBS/PBS data

A file of study participants including study identification number and the approved consent forms will be sent to Services Australia for obtaining the claims history for MBS and PBS data.

4.8 Data flow and storage

Table 1 summarises the data sources and flow:

Data	Туре	Source	Custodian	Flow	Ethics/ governance considerations
Community Pharmacy registration data	Identified, + participant study ID	Community pharmacy (MedAdvisor)	- MedAdvisor -The George Institute (TGI) -The University of Newcastle (UoN)	-MedAdvisor send identified data to TGI and UoN	-University of Newcastle (UoN) HREC approval -Data access agreement between UoN, TGI and MedAdvisor
Participant 7- day follow-up data	Deidentified, + participant study ID	GDS form hosted by TGI	-TGI	-Data retained by TGI and shared with UoN	-UoN HREC approval
Implementation data	Pharmacy ID Participant study ID	Community pharmacists and participants	-UoN -TGI	-Checklists entered into pre- prepared REDCap form -Interviews professionally transcribed and stored on UoN/TGI password protected server -Data retained by UoN/TGI and not sent to other parties	-UoN HREC approval
NSW Health data	Deidentified, + participant study ID	TGI	-TGI -NSW Health	-TGI sends NSW Health a list of participants -NSW Health sends to Centre for Health Record Linkage (CHeReL) -CHeReL sends deidentified data with participant ID to TGI	-UoN HREC approval -NSW Health establishes a Public Health Register -Data access agreement between TGI and NSW Health
MBS/PBS	Identified data + participant study ID	Community pharmacy (MedAdvisor)	-TGI -Services Australia	-Pharmacy/ MedAdvisor sends paper/electronic Services Australia consent form to TGITGI prepares file including participant ID to send to services Australia with electronic/ scanned consent forms -Services Australia	-UoN HREC approval -Services Australia External Request Evaluation Committee

sends deidentified
data with participant ID to
TGI

MedAdvisor is a ISO27001 credentialled company. This information security standard governs the company's handling of how personally identifiable information and health data is securely recorded and stored. Information is accessed by researchers via an extension of the company's information security management system and will be underpinned by a data sharing agreement. Functionally, researchers will be provided data via a secure machine to machine integration or a secure machine to human process. The company utilises the secure transfer software Kiteworks for this purpose. Pharmacy data is restricted within the pharmacy in alignment with the company's existing Pharmacy Licencing Agreement and the ISO27001 framework. The company offers on-premises software to support this data handling.

The George Institute policies pertaining to the secure transfer and storage of study materials and data will be followed. TGI's secure infrastructure is physically located in an ISO 27001 certified data centre in Sydney. Technical controls include access via encrypted network connections, multi factor authentication, data storage on encrypted disks, encryption of all offsite backups, discretionary access controls on project data folders, micro-segmented next generation firewalls, together with a Security Information and Event Management system monitoring network traffic and scanning for Indicators of Compromise. Associated procedural controls are captured in standard operating procedures and Work Instructions.

Pharmacies, pharmacists, and patients will provide consent for data to be transferred from MedAdvisor to the research team.

4.9 Outcomes

Primary outcomes

Primary outcomes will be accessibility and acceptability of the service (based on self-report at 7-day follow up). This will be a composite measure based on patient self-reported data. It includes seven items adapted from existing questionnaires, including a validated questionnaire for perceived service quality in community pharmacies (two items) and studies of pharmacy prescribing for oral contraception, and other medications [1-6]. It will cover the following domains: (a) trust and confidence in health and medical advice provided, (b) convenience, (b) privacy during discussion with pharmacy, and (b) overall satisfaction. Each item is scored on a 7-point Likert scale. Each domain will be equally weighted, and an aggregated score calculated and scaled to a maximum score of 100.

Secondary outcomes

- **On time dispensing rates**: 36 months pre and 12 months post introduction of the intervention (assessed using the proportion of days covered method using PBS data) [40].
- **Primary care utilisation:** MBS records will be used to measure use of general practice services prior up to 36-months pre and 12 months post introduction of the intervention date (MBS data).
- **Safety outcomes**: Adherence rates to Clinical management protocols (assessed by practice change facilitators conducting regular pharmacy monitoring and inspection of data from the patient consultation IT system), hospitalisation for potential pill-related adverse events (e.g., thromboembolic disease) (NSW Health data), rates of STI tests undertaken (MBS pathology data) and adverse events.
- **Implementation outcomes**: Implementation outcomes will also be assessed to examine the fidelity, reach and adoption of the new service, and barriers and facilitators to implementation.

• **Economic outcomes:** Results from the economic analysis will be expressed as (1) net benefit in terms of implementation costs and cost savings arising from more efficient treatment pathways; and (2) cost-consequence results accounting for patient experience measures, relevant safety outcomes and implementation measures. This will be assessed using multiple data sources including MBS records for 36 months pre and 12 months post introduction of the intervention.

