4.5.2 Pharmacy consultation

The pharmacist will undertake a structured consultation with the patient in the community pharmacy guided by an IT program applying one of two clinical management protocols (Combined Oral Contraception and Progestogen-Only Contraception) which encompasses the recommendations from the Australian Therapeutic Guidelines. The clinical management protocol has been subject to co-design between community pharmacists and senior general practitioners with advice from a subject matter expert. This consultation is anticipated to take 10 minutes.

The intervention is provided under the NSW Health Authority allowing participating NSW pharmacists to supply medications as part of the trial. For the ACT, a discretionary licence will be approved for participating pharmacies.

The structured consultation is summarised in Box 1.

BOX 1

- Participant eligibility assessment, in which the pharmacist will assess if the patient meets the inclusion/exclusion criteria to participate in the study.
- Service offering, during which the pharmacist will explain the features of the study and will ask the patient if she/they is willing to participate.
- Electronic provision of the Patient information sheet and informed consent form.
- Patient's clinical assessment. During the assessment the pharmacist will elicit relevant clinical information, including medical conditions, medication history, in line with agreed clinical management protocols. If the patient is a usual patient of the pharmacy, their medication dispensing history may be checked on the computer record, if not the patient medications will be asked. Further information may be obtained from the patients' Electronic Health Record (EHR). Viewing a patients EHR is legally and professionally allowed by pharmacists, with patient consent.
- Clinical measurements of Blood Pressure and BMI will be documented at the initial patient consultation.
- After the clinical assessment, the pharmacist will use one of two clinical management protocols to proceed to resupply.
- Pharmacists may supply a continuation of the oral contraceptive pill (minimum 1 month, and up to 12 months' supply) provided the patient has seen a general practitioner (or other authorised prescribing health care professional in the last 2 years. Pharmacists are not permitted to initiate or change therapy.
- Non-pharmacological management may include:

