4.5.4 Considerations for the delivery of the intervention

Cost to patients

NSW - The cost of the consultation with patients (\$20) will be paid for by the NSW Government to pharmacies, irrespective of the outcome of the consultation. The patient will meet out of pocket expenses for any medicines or products provided.

ACT - The cost of the consultation with patients will be paid for by the patient receiving the service to pharmacies, irrespective of the outcome of the consultation. The patient will also meet out of pocket expenses for any medicines or products provided.

Legislative considerations

NSW - The legislative approval required for the trial has been developed and executed by the NSW Ministry of Health.

ACT - The ACT legislation process has been determined by the acting Chief Pharmacist in ACT. Whilst in NSW the Chief Medical Officer signs an Authority for the change, a licence application will need to be made by participating pharmacies in ACT. The discretionary licence (available via PDF) would be issued to authorise the 5 pharmacies in the ACT to participate in the trial (Appendix 29). Further details on the licensing can be found on the ACT website: https://www.health.act.gov.au/businesses/medicine-and-poisons-licences-and-permits

Professional indemnity for pharmacists

Pharmaceutical Defence Limited (PDL) is the major provider of professional indemnity and will cover pharmacists as part of their normal indemnity for delivery of this service. Guild Business will cover the liability from the perspective of the pharmacy premises.

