4.6.2 Participant (patients) self-reported data

Participants will be assessed at the registration visit (consultation) described above and this will include basic demographic and clinical information. Those assessed as eligible to participate in the trial will be followed up at Day 7 post registration to assess outcomes. This will include a brief survey administered by the George Institute either via SMS message or phone call with a link to a case report form using George Data Systems (GDS). Appendix 19 provides the case report form for the 7-day follow-up visit.

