4.6.5 Medicare Benefits Schedule (MBS) and Pharmaceutical Benefits Scheme (PBS) data

Participants will be requested at registration to provide consent to access their MBS and PBS data for the evaluation. The Services Australia approved patient and information consent form (Appendix 23) will be used to seek consent. Participants will have the option of authorising Services Australia to provide their claim history for MBS, PBS or both.

As the study will be examining how the use of this service impacts consistency of oral contraception adherence, a 3-year lookback will be requested for PBS data. This will allow analysis of prescribing and dispensing habits over multiple prescribing and refill cycles and to assess discontinuation rates pre and post introduction of the service as a proxy to assessing adherence gaps.

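### A supply at or near 12 months can fill the 12-month post window, so proportion of days covered and refill-based discontinuation cannot show whether the woman continued

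*Protocol*

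**What the plan says.** Section 4.9 of the protocol lists on-time dispensing as a secondary outcome, measured over "36 months pre and 12 months post introduction of the intervention (assessed using the proportion of days covered method using PBS data"). Section 4.6.5 gives the purpose. The study is "examining how the use of this service impacts consistency of oral contraception adherence", and the three-year PBS lookback is requested partly "to assess discontinuation rates pre and post introduction of the service as a proxy to assessing adherence gaps". The same section expects the history to span several cycles: "This will allow analysis of prescribing and dispensing habits over multiple prescribing and refill cycles".

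Section 4.5.2 (Box 1) sets the length of a trial supply: "Pharmacists may supply a continuation of the oral contraceptive pill (minimum 1 month, and up to 12 months' supply").

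Four other places bear on the point:
- Section 4.4.2 admits only women who come for a continuing supply and have been stable on their pill, without interruption, for two years.
- Section 4.6.1 has the pharmacist record the quantity and date of each dispensing.
- Section 4.6.2 schedules one quantitative self-report. Participants "will be followed up at Day 7 post registration to assess outcomes".
- Section 4.10.1 adjusts for age, comorbidity count, earlier primary care use and SEIFA, but not for months supplied.

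**The concern.** PDC counts days for which pills were supplied. It serves as a proxy for continued use because each refill shows that the woman came back for more. That link fails when one supply lasts as long as the window in which refills are looked for: she cannot be late, and she cannot be seen to stop.

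The service itself affects how much is supplied at once, so the post-entry score can vary with the quantity handed over while pill taking stays the same. If PDC is then read as continuation, women who stopped after a long supply are counted as fully or almost fully covered, and the service looks better at sustaining use than the data can show.

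**Working it through.** The protocol gives no expected PDC, pack size or gap rule, so there is no figure to reproduce. The check is direct arithmetic.

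**Inputs from the protocol.** Supply of 1 to 12 months at one consultation (section 4.5.2). Post window of 12 months, taken as W = 365 days (section 4.9).

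**Assumptions.** One fill at the start of the window. The woman stops at day 7 and never refills. A month's supply is either one 28-day pack or one calendar month (365/12 days). The permitted gap g before discontinuation is declared is 30, 60 or 90 days. The supply appears in the data used.

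**Step 1: coverage.** True coverage is 7/365 = 1.9%. Measured PDC = min(S, W)/W, where S is the days supplied.

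| Single fill | 28-day packs | Calendar months |
|---|---|---|
| 1 month | 28/365 = 7.7% | 8.3% |
| 4 months | 112/365 = 30.7% | 33.3% |
| 6 months | 168/365 = 46.0% | 50.0% |
| 9 months | 252/365 = 69.0% | 75.0% |
| 12 months | 336/365 = 92.1% | 100% |

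Thirteen 28-day packs give 364/365 = 99.7%.

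**Step 2: discontinuation.** A stop is seen only if S + g ≤ W. It is hidden when S exceeds 365 − g: above 335 days for g = 30, 305 for g = 60 and 275 for g = 90. Twelve 28-day packs (336 days) are hidden under all three, though for g = 30 by a single day (336 + 30 = 366). Twelve calendar months are hidden under all three with room to spare. A six-month fill is seen under all three; with calendar months and the longest gap, 182.5 + 90 = 272.5, which is below 365.

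**Step 3: where the window starts.** Section 4.9 counts from introduction of the intervention, which could mean each woman's consultation or the launch of the service. If it means launch, a woman enrolled at month e needs only 12 − e months' supply to fill what remains: 6 months if enrolled at month 6, 3 months if enrolled at month 9.

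**Step 4: is it repaired elsewhere?** The Day 7 survey comes too early to show later stopping. The interviews are qualitative and cover a sample. The regression does not include months supplied.

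**The case against.** Several points on the other side stand.

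- **Supply mix.** The protocol gives a range of 1 to 12 months and no distribution. The fault is confined to supplies near 12 months, or to those that fill the rest of a launch-anchored window.
- **Possession, not ingestion.** No dispensing measure observes pill taking. Section 4.9 names the outcome as dispensing, section 4.6.5 calls discontinuation a proxy, and discontinuation is not listed as an outcome in section 4.9. Fewer gaps in possession may also be a real access benefit. So PDC is worth keeping; what fails is reading it as continuation.
- **PBS recording.** The 92% to 100% score requires the trial supply to be in the data. The protocol does not say that it will be. For NSW it says only that "The patient will meet out of pocket expenses for any medicines or products provided", which does not settle the matter. If supplies are absent, the same woman scores near 0% after entry, which is a separate and opposite fault.
- **SAP content.** A grace period can be left to a SAP. The method, data source and 12-month window cannot be treated that way here, because the protocol already fixes them and they produce the problem.

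A reader might go further and infer that PDC must rise from pre to post by a calculable amount, or that stops which were visible before entry become invisible after it. The documents do not support that. Women who had stopped for good could not enter, and eligibility selects the last 24 of the 36 pre-entry months for continuity. The length of a usual refill cycle before entry is not given either. Late refills before entry could still allow some rise, but its size cannot be derived.

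**Conclusion.** The concern holds in a limited form. For a woman supplied at or near 12 months, with the supply recorded, PDC is about 92% to 100% and discontinuation cannot be observed in the window, whatever she does after day 7. With a single six-month fill, PDC is about 46% to 50% and the stop is visible.

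Because the cohort consists of established continuous users, the main effect is to mask discontinuation after entry. The pre/post contrast then depends partly on the quantity handed over. No size can be put on the cohort-level bias, since the mix of supply lengths and the stopping rate are not stated.

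The figures rest on the assumed pack size, the assumed gap rules and recording of the supply in the data used. The primary outcome is unaffected. Section 4.5.2 and the outcome in section 4.9 should be reconciled through the outcome definition.

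**What to change.** In section 4.9:

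1. Keep PDC, describe it as possession, and report it by months supplied. Do not interpret it as continuation where the supply spans the window.
2. Add on-time renewal. For each supply, before or after entry, derive the run-out date from date and quantity, and score whether the next supply occurs within a fixed grace period. Section 4.6.1 already collects both items for trial supplies; the PBS history would have to provide them for earlier ones.
3. Treat any supply whose run-out plus grace period falls beyond the available data as censored for discontinuation, not as continued use, and report how many there are.

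The cost is outcome wording and some programming, plus one of two drawbacks: fewer women evaluable for discontinuation, or a later data extract that may need an updated data approval. No change to the supply rule is proposed.

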Barriers to access are one reason for inconsistent or non-use of contraception [9, 10]. There are several barriers such as the requirement for a prescription that can prevent women from continuing their contraceptive method of choice [10]. As stated in The Senate Community Affairs References Committee; Ending the postcode lottery: Addressing barriers to sexual, maternity and reproductive healthcare in Australia (May 2023), other key reported obstacles include: regulatory restrictions limiting the role of pharmacists, inadequate incentives for medical practitioners to bulk-bill, contraceptives not available on the PBS, high financial costs, and limited access in rural and remote regions and First Nations communities [10].

Expanding access to contraception allows individuals to safely space and limit their pregnancies and reduces unintended pregnancies, maternal morbidity and mortality [8, 10]. It is accepted at an international level that there is significant potential to increase access to prescription contraceptives in a cost-efficient manner by expanding the scope of practice among a range of allied health professionals, including pharmacists, who with the appropriate training, could help provide contraceptive care [11]. Studies have established that women can self-screen and non-physicians can safely assess for medical contraindications to OCP use [12-16].

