4.6 Data sources

4.6.1 Community pharmacy data

During implementation of the intervention, information on health service delivery and program activities will be routinely captured in a case registration form by community pharmacists using the MedAdvisor application which is built into pharmacy software systems. For the purposes of evaluation and study participants (pharmacies and patients) will be assigned a unique study identification number.

The following information will be collected by the community pharmacists:

- 1. Name of patient
- 2. Age
- 3. Address
- 4. Documented weight, height, and BP on initial contact.
 - o BP and BMI will be documented at the first consultation
- 5. The name, dose, quantity, and manufacturer of the hormonal contraceptive dispensed or administered by the pharmacy
- 6. The date of dispensing
- 7. Name of prescriber
- 8. The name, address, telephone number of the pharmacist (address and phone number of the principal place of practice of the pharmacist is sufficient)

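### Dispensing and discontinuation outcomes rest on PBS data alone, but the protocol does not show that pills supplied by trial pharmacists appear there

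*Protocol*

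**What the plan says.** Section 4.9 (Outcomes) lists on-time dispensing rates first among the secondary outcomes and fixes both method and source: "36 months pre and 12 months post introduction of the intervention (assessed using the proportion of days covered method using PBS data". Section 4.6.5 gives the reason for a three-year PBS lookback, which includes "to assess discontinuation rates pre and post introduction of the service as a proxy to assessing adherence gaps". Neither section names a second data source for these measures.

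On the supply itself, section 4.5.2 places the NSW service under an Authority "allowing participating NSW pharmacists to supply medications as part of the trial", with a discretionary licence playing that part in the ACT. It allows a wide range of quantities: "Pharmacists may supply a continuation of the oral contraceptive pill (minimum 1 month, and up to 12 months' supply". On payment, section 4.5.4 says for NSW "The patient will meet out of pocket expenses for any medicines or products provided" and has the same rule for the ACT.

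The trial supply is also recorded elsewhere. Under section 4.6.1 the pharmacist enters in MedAdvisor "The name, dose, quantity, and manufacturer of the hormonal contraceptive dispensed or administered by the pharmacy" and the dispensing date. Section 4.7.1 sends the MedAdvisor extract to the research team with the study identification number. Table 1 in section 4.8 shows the PBS data returning with the participant ID. The protocol does not bring these supply records into the PDC or discontinuation measures.

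**The concern.** The exposure in this study is itself a supply of pills. A measure of pill coverage that might not see that supply could make women who use the service appear to have stopped or lapsed. The error would be absent before enrolment and present afterwards, and it would grow with the quantity supplied. The covariates in section 4.10.1 (age, comorbidity count, prior primary care use, SEIFA) could not remove it, because it comes from the exposure and not from who takes part.

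Consistent use of the pill is the stated reason for requesting three years of PBS data, and better continuation is part of the rationale in section 3.1. If capture is incomplete, a service that improves continuation could be reported as harming it.

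**Working it through.** The protocol gives no PDC figure, target or power calculation for this outcome, so there is nothing of its own to reproduce. The check is direct arithmetic.

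**Inputs**
- Post period: 12 months (section 4.9).
- m, months of pills supplied by the trial pharmacist and used within those 12 months: 1 to 12 (one supply may be of any length in that range, section 4.5.2).
- c, the share of that supply that leaves a PBS record: not given in the protocol, so taken over its full range, 0 to 1.
- Assumed: the woman is truly covered every day (true PDC 1.0), and all her other pills are visible in PBS.

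**PDC as PBS data alone would show it**

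PBS-only PDC = (12 − m + c·m)/12, so the error is −(1 − c)·m/12.

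| m (months) | c = 0 | c = 0.5 | c = 1 |
|---|---|---|---|
| 1 | 0.917 | 0.958 | 1.0 |
| 3 | 0.75 | 0.875 | 1.0 |
| 6 | 0.50 | 0.75 | 1.0 |
| 12 | 0.00 | 0.50 | 1.0 |

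**Effect on a pre/post change (assumed example)**

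Suppose true PDC rises from 0.85 to 0.95, c = 0, and a share s of the covered post days comes from trial supply. The observed change is 0.95(1 − s) − 0.85.
- s = 1/12: 0.871 − 0.85 = +0.02
- s = 0.25: 0.7125 − 0.85 = −0.14
- s = 0.50: 0.475 − 0.85 = −0.375
- Observed change of zero: s = 1 − 0.85/0.95 = 0.105. With 0.95 × 12 = 11.4 covered months, that is 0.105 × 11.4, or about 1.2 months of trial supply.

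With no capture, then, little more than one month of trial supply per woman would hide a true gain of 10 percentage points.

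**With the trial records added**

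Counting PBS dispensings and MedAdvisor trial supplies together, each supply once, gives (12 − m + m)/12 = 1.0 for every m and every c. The result does not depend on the unknown c.

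**A limit of the merge**

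Trial supply records do not exist for the pre period. A woman fully covered throughout by a pill that never appears in PBS would score 0 before and m/12 after on the merged measure, an error in favour of the service. This is why the fix also restricts the comparison to women whose pill is visible in PBS beforehand.

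**The case against.** The strongest objection is that the key premise is missing from the protocol. Nothing says that a trial supply leaves no PBS claim. Paying out of pocket fits a PBS co-payment as well as a full private price, and the Authority and the licence, which might settle the matter, are not reproduced in the protocol text. This stands. A reader might infer that using the service will look like non-adherence, with a spurious fall of 8 to 100 percentage points. The documents do not support that as a statement of fact: those figures hold only at c = 0, and at c = 1 there is no bias. The largest figure also needs a 12-month supply that fills the whole window, and the protocol does not say how common such supplies will be.

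Section 3.1 lists "contraceptives not available on the PBS" among access barriers, which might be read as evidence that trial pills are invisible in PBS data. It is a general background statement about access, not a description of the approved pills or of trial supply. A pill outside the PBS would also be missing from PBS data both before and after enrolment, which is a coverage limit and not a post-period error.

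A reader might also infer that the economic analysis shares the problem, with pills moving from PBS to private payment and so appearing as a saving. Section 4.10.3 does not support this. It uses PBS listed prices to value medication, without saying that use is counted from PBS claims alone. It takes intervention resource data from pharmacies and patients, and it includes patients' own medicine costs in the societal perspective. In the health-service base case, a cost that moves to the patient is a real saving to that payer.

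What remains is that the protocol fixes one source for two outcomes without showing that this source sees the exposure, while a record of the exposure is already collected.

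**Conclusion.** The point holds in conditional form. PBS data are the only named source for PDC and discontinuation, and the protocol does not establish that they contain the pills supplied in the trial. If capture is incomplete, the bias runs against the service. For a fully covered woman it ranges from nothing at full capture to a loss of 0.083 (1 month) to 1.0 (12 months) in PDC at zero capture, and half those losses at half capture. These sizes assume that her other pills are all visible in PBS and that the trial supply is used within the 12 months. For discontinuation the direction is the same; the size depends on the gap that is taken to mean stopping.

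Only secondary outcomes are involved. The primary outcome, self-report at day 7, is unaffected, and no sample-size or error-rate figure changes. The correction is still worth making before analysis, because it is cheap and gives the right answer for PBS-visible pills whether or not trial supplies reach PBS.

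**What to change.** 1. State in the protocol or SAP whether trial supplies in NSW and in the ACT, and each approved pill, generate PBS records.
2. Define PDC and discontinuation on PBS dispensings linked by study ID to MedAdvisor trial supplies, with days covered taken from date, product and quantity. Count a supply found in both sources once; otherwise a method that carries surplus pills forward would inflate post-period coverage.
3. Confirm that the MedAdvisor extract includes every trial supply in the 12 months. Section 4.7.1 describes it in terms of the registration visit.
4. Report the pre/post comparison, at least as a sensitivity analysis, limited to women whose pill is visible in PBS in the pre period, and give the proportion excluded. PBS consent is optional under section 4.6.5, so report the number without PBS data separately.

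The cost is a change of wording and one extra data merge. If the check in item 3 is satisfied, no new data collection is needed.
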